Since the original approval of the multi-channel cochlear implant (1985), advances in technology, electrode design, speech coding strategies and surgical techniques have occurred at a relatively rapid rate which have led, and continue to lead to significant improvements in cochlear implant recipient performance. Just as changes to technology and technique have ensued, so has that of the profile of the cochlear implant candidate.

More recently, this standard of care treatment option has been suggested and explored for a patient population not previously considered implant candidates as a means to restore binaural hearing input. The patient population is that of single sided deafness or asymmetrical hearing loss who present with unilateral severe-to-profound hearing loss and much better hearing in the opposite ear. The underlying supposition is that such patients are able to function effectively with the better hearing ear alone even if that ear requires some amplification. However, patients with single-sided deafness or asymmetrical hearing experience considerable communicative difficulties in everyday listening environments and quality of life. This is well supported in peer-reviewed literature and research (Wie et al. 2010; Noble et al. 2008).

Historically, patient populations with substantial asymmetrical hearing loss have been underestimated as to the level of handicap this type of loss actually poses. Patients with single-sided deafness function with unilateral hearing input which can affect speech understanding, conversing in noisy environments, sound localization, (Arndt et al., 2011), directionality and spatial awareness due to the monaural acoustic stimulation. Unilateral hearing additionally demands higher concentration for listening, leading to rapid fatigue, potential misunderstandings, frustration and distractibility (Wie et al., 2010).

Treatment options for asymmetrical hearing loss have included conventional hearing aid systems (i.e. CROS or BICROS – contralateral routing of signal) or an osseointegrated/bone – anchored system (i.e. BAHA™; Ponto). While these options offer a solution, there are substantial limitations. Specifically, the current conventional options capture and route sound

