received at the poorer ear and deliver at audible sensation levels to the better hearing ear and/or functioning cochlea (Roland et al., 2011; Mueller et al., 1990; Niparko et al., 2003; Lin et al., 2006) either via bone conduction or contralateral routing of the signal. However, these types of devices do not provide and/or restore *binaural* auditory input. This precludes any benefit of binaural hearing system and respective binaural auditory processes (i.e. sound localization, spatial awareness and/or improved speech perception/understanding in noise).

Another relevant aspect related to hearing loss and an asymmetric hearing loss or single-sided deafness clinical population that has been well documented in peer-reviewed studies is that of tinnitus. Tinnitus is often concomitant, and in many cases debilitating, with severe-to-profound hearing impairment (Vermeire et al., 2009; Buechner et al., 2010; Hansen et al., 2013). Conventional treatment options such as CROS or osseointegrated systems have been reported as unsuccessful in the treatment and suppression of tinnitus. This is in part related to an inability to sufficiently deliver acoustic input to the poorer ear to aid in suppression or diminution given the level of hearing loss severity; and that the conventional (i.e. CROS or BICROS) option or direct bone conduction stimulation does not stimulate the poorer ear as everything routes to the better hearing side.

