9.0 Study Visits

Baseline Visit

Signed Informed Consent is to be obtained prior to the conduct of any study procedures. Baseline information consists of collection of participant demographics, hearing and pertinent medical history, hearing history (i.e. etiology and onset of hearing loss, date of birth, gender, duration of hearing loss, amplification use). With respect to amplification use, the licensed/certified hearing care professional will determine if a potential study participant has had an adequate and/or appropriate trial using conventional amplification available for single-sided deafness and asymmetrical hearing loss.

The following test measures are administered at the Baseline Visit:

Audiometric Testing:

- Unaided air-conduction thresholds using insert earphones at 250, 500, 1000, 2000, 4000 and 8000 Hz; unilateral, each ear. Clinical masking as appropriate.
- Unaided bone-conduction hearing thresholds at 500, 1000, 2000 and 4000 Hz; unilateral, each ear

Speech Perception Testing:

- Separate Ear CNC Word Test Two lists of 50 words tested in the participant's everyday listening condition for that ear, thus:
 - If the test ear is unaided (participant does not utilize conventional amplification such as a hearing aid, CROS, BICROS or osseointegrated system), measurement of CNC words using insert earphones presented at 60 dBA will be conducted.
 - If the test ear is aided with conventional amplification (i.e. hearing aid, CROS, BICROS or osseointegrated system), measurement of CNC words is conducted in soundfield at 60 dBA (Target 0° Azimuth) with the plug and muff method in use for the non-test ear (better hearing ear) to eliminate from potential cross-over and/or contribution to the outcome.
- AzBio Sentence Test in Noise Two lists presented in the following soundfield conditions at 60 dBA with a +5 dB SNR using speech-spectrum noise in the participant's bilateral, everyday listening condition. Note: Participants may or may not be aided in one or both ears thus, testing may be aided or unaided or a combination during AzBio Sentence test administration). The following test conditions will be conducted:

- Speech Front, Noise Front (Target and Noise 0° azimuth)
- Speech Front (0° azimuth), Noise directed to the ear to be implanted (90° or 270° azimuth)
- Speech Front (0° azimuth), Noise directed to the contralateral/non-implanted ear (90° or 270° azimuth)

Lateralization Testing:

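### For users of CROS, BICROS or osseointegrated devices, baseline CNC of the ear to be implanted is tested through a device that routes sound to the other ear, which leaves the score unchanged or raises it

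*Combined protocol and SAP*

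**What the plan says.** **How baseline CNC is taken.** Section 9.0 (Baseline Visit) has two branches for separate-ear CNC, each with two 50-word lists at 60 dBA.

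- The insert-earphone branch applies "If the test ear is unaided (participant does not utilize conventional amplification such as a hearing aid, CROS, BICROS or osseointegrated system"). Users of routing devices are therefore outside it.
- The other branch applies "If the test ear is aided with conventional amplification (i.e. hearing aid, CROS, BICROS or osseointegrated system), measurement of CNC words". It is run in soundfield "with the plug and muff method in use for the non-test ear (better hearing ear"), so as to keep that ear out of the result.

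**Who may be in the second branch.** The Glossary accepts CROS, BICROS and osseointegrated systems as a possible preoperative everyday condition of the poorer ear. Section 4.0 introduces the first two with "Treatment options for asymmetrical hearing loss have included conventional hearing aid systems (i.e. CROS or BICROS" and adds bone-anchored systems. Section 9.0 has a hearing professional judge whether the candidate has "had an adequate and/or appropriate trial using conventional amplification available for single-sided deafness and asymmetrical hearing loss", and the baseline record includes "duration of hearing loss, amplification use".

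**What the devices do.** Section 4.0 describes these options as routing sound "received at the poorer ear and deliver at audible sensation levels to the better hearing ear and/or functioning cochlea". A later sentence there says that CROS or BICROS, or "direct bone conduction stimulation does not stimulate the poorer ear as everything routes to the better hearing side".

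**What the score is for.** It decides the ≤30% criterion for the ear to be implanted (Synopsis and Section 7.4). It is also the pre-implant comparator for the 12-month CNC score of that ear (Section 11.0, item 1). Section 8.3.2 makes CNC the main speech metric for both uses.

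**Safeguards.** Section 8.3 provides for masking where needed to limit the better ear's contribution. It names no device, and no section tells sites to remove or switch off a routing device for single-ear CNC.

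**The concern.** The test branch counts the poorer ear as aided by a device that, on the protocol's own account, works through the other ear. Plug, muff and any masking are then applied to the very ear that receives the routed signal. How much of that signal gets through could differ between devices and between sites.

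Two things are at stake for these users. A candidate whose poorer ear recognises almost nothing could score above 30% through the better cochlea and be turned away. A candidate who is enrolled could carry a baseline that is too high, so that the individual and mean CNC gain in the implanted ear comes out too small.

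**Working it through.** The plan gives no power, effect size or derived sample size, so there is no figure of its own to reproduce. The check sets the sections against each other and then bounds the size.

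**1. The two cases.** Take a routing-device user tested under the second branch of Section 9.0, and compare with the same set-up with the device off.

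- *Routed signal blocked.* By Section 4.0 the device adds nothing at the poorer ear. The result is in effect that ear's unaided soundfield score. It is mislabelled as aided, but it does measure the named ear. Error: zero.
- *Some routed signal survives.* The better cochlea hears some words and the score rises. Error: upward.

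This takes routed speech to add correct responses rather than to interfere with the poorer ear. On that basis no case gives a score below the device-off score.

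**2. Ceiling on the error in mean gain.** Inputs: an enrolled user has a recorded baseline of at most 30% (Synopsis, Section 7.4); the lowest possible device-off score is 0; the number of subjects is up to 15 (Synopsis, Section 10.0) or up to 20 (Section 7.3).

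Error in mean gain per affected enrolled user = (recorded baseline − device-off score) / N.

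- N = 15: (30 − 0)/15 = 2.0 points
- N = 20: (30 − 0)/20 = 1.5 points

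For three such users the ceilings are 3 × 2.0 = 6.0 and 3 × 1.5 = 4.5 points. If contamination is 10 points rather than 30, one user shifts the mean by 10/15 = 0.7 points. Both values of N are maxima. With fewer subjects analysed, the ceiling per user is 30/n.

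**3. Eligibility, as an illustration.** Inputs: 2 × 50 = 100 words (Section 9.0), treated as independent; the true score p obtained through the device is *assumed*, because the documents give none. P(pass) = P(X ≤ 30) for X binomial (100, p).

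| Assumed p through the device | P(score ≤30%) | P(fails criterion) |
|---|---|---|
| 20% | 0.994 | 0.006 |
| 25% | 0.896 | 0.104 |
| 30% | 0.549 | 0.451 |
| 35% | 0.173 | 0.827 |
| 40% | 0.025 | 0.975 |
| 50% | <0.001 | >0.999 |

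The chance of failing runs from almost none to almost certain over this range. The table shows that exclusion is possible. It does not estimate how often it happens.

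**The case against.** The strongest reply is that plug, muff and masking are there to remove the better ear. If they succeed, the routed signal goes too, and what remains is the poorer ear's own score, close to what a device-off test would give. That stands: only surviving routed signal does harm. A reader might infer that the rule can never measure the ear it names. The documents do not support that.

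A reader might also infer that the error could run either way, or could exaggerate implant benefit. It cannot, on the reasoning above. A baseline that is too high makes entry harder and gain smaller, so the error is conservative.

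Nor do the documents show that many participants are affected. A past trial of conventional amplification is not everyday use. A candidate who tried CROS and gave it up is unaided and goes to insert earphones. The Glossary says only that these devices may be the everyday condition.

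Other points in the plan's favour also stand. Severity of loss is set separately by the pure tone average, individual results are tabulated (Section 10.0), and amplification use is recorded, so affected users can be identified.

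Three things remain. Masking as needed does not instruct a site to switch the device off. Identifying a user afterwards does not recover the device-off baseline or a candidate already excluded. And although the sentence denying stimulation of the poorer ear sits in a passage on tinnitus, the routing description earlier in Section 4.0 is general and agrees with it.

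**Conclusion.** The conflict between Sections 4.0 and 9.0 is real and the point holds, but it is minor. It concerns only participants whose everyday device for the poorer ear is CROS, BICROS or osseointegrated; their number is not given and may be zero. For them the baseline single-ear CNC score is right or too high relative to a device-off score. The possible effects are failure of the ≤30% criterion by an eligible ear and an understated CNC gain, with the ceiling of 2.0 points of mean gain per affected enrolled user at 15 subjects or 1.5 at 20.

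That ceiling assumes a device-off score of zero and a recorded baseline exactly at the limit. The actual size is unknown, because the documents do not say how much routed signal survives. No formal hypothesis is tested (Section 10.0), so no error rate is involved. Bilateral AzBio, lateralization and SSQ do not depend on this score. Unaided ears and ears wearing a hearing aid are not affected.

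**What to change.** Reconcile the Glossary, Section 4.0, Section 7.4 (with the Synopsis) and Section 9.0 on the single-ear CNC condition:

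- State in Section 9.0 that, for single-ear CNC of the ear to be implanted, devices that route sound to the other ear are removed or switched off, and that the aided branch is only for a hearing aid worn in the test ear.
- Test routing-device users device-off by one method fixed for all sites. One choice is soundfield with plug and muff, and contralateral masking where needed. This matches the 3- and 6-month procedure; the 12-month entry does not repeat plug and muff, though Section 8.3 covers it in general. The other is the existing insert-earphone branch, which adds a difference in method between baseline and follow-up that unaided participants already have.
- Use that score for the ≤30% criterion and as the pre-implant comparator.
- Keep the everyday device for bilateral AzBio and lateralization, and flag the baseline device in the individual listings.

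No new equipment or visit is needed. The costs are:

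- A formal amendment with the reviews set out in Sections 14.4.1 and 22.0.
- A single-ear baseline that is no longer the everyday condition for these users.
- Probable near-floor baseline scores. This is an inference: the ear has a pure tone average of about 70 dB HL or worse and would be tested unaided at 60 dBA. The ≤30% limit would then screen little for these users, and their measured gain would lie close to the 12-month score.

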10.0 Statistical Methods

General Considerations: Statistical Methods and Sample Size

Individual outcomes will be compared across pre- and postoperative test conditions for audiometric and speech performance outcomes. No formal statistical hypothesis will be tested. At a minimum, individual data/outcomes will be tabulated and summarized for audiometric and speech performance outcomes to establish numbers of subjects showing improvement, no change or decrease in performance. Descriptive statistics may consist of counts, means, median and standard deviations, percent and relative frequency for categorical variables (i.e.

questionnaire). The proposed sample size the Sponsor is aiming to recruit for participation of up to 15 total subjects is deemed sufficient for this feasibility study.

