7.4 Inclusion and Exclusion Criteria

General Inclusion criteria:

- Ability to provide Informed Consent
- 18 years of age or older
- English language proficiency (to be confirmed via case history as having graduated 8th grade level)
- Willingness to participate in all scheduled procedures outlined in the protocol
- Willingness to use an approved cochlear implant signal processing strategy in an everyday listening program during study

Audiometric Inclusion criteria:

Ear to be Implanted:

- Severe-to-profound sensorineural hearing loss (>70 dB HL) as defined by the pure tone average for 500, 1000, 2000 and 4000 Hz
- CNC word recognition score up to ≤30% (tested in subject's everyday listening condition for that ear)
- Duration of severe-to-profound sensorineural hearing loss (>70 dB HL) >3 months and ≤10 years in the ear to be implanted only

Contralateral (non-implanted) ear:

- Up to a moderate sensorineural hearing loss (<70 dB HL) as defined by the pure tone average for 500, 1000, 2000 and 4000 Hz
- CNC word recognition score >30% (tested in subject's everyday listening condition for that ear)

Exclusion Criteria:

- Previous experience with a cochlear implant
- Cochlear malformation or obstruction (i.e. ossification) that would preclude full insertion of electrode array in the *ear to be implanted*
- Medical or psychological conditions that contraindicate surgery or impact the ability to manage an implanted device or the study related procedures as determined by the investigator
- Diagnosis of auditory neuropathy/dys-synchrony in either the ear to be implanted or the contralateral ear
- Active middle-ear disease/infection in the ear to be implanted
- Unrealistic expectations regarding potential benefits, risks and limitations inherent to implant surgical procedures as determined by the investigator
- Unwillingness or inability of subject to comply with all investigational requirements as determined by the investigator

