8.3 Test Metrics or Procedures

The monosyllabic CNC word test will be used as the primary test metric for preimplant candidacy determination and follow-up postimplant performance assessments in the treated ear. The AzBio Sentence test in noise will be used as the primary test metric to assess the binaural hearing condition (implanted + non-implanted ear) performance pre-to-postoperatively.

Given the asymmetrical clinical population for which this feasibility study is being conducted, standard audiometric clinical masking procedures during audiometric and speech perception metrics will be applied as needed to reduce any potential contribution of the better hearing ear during these assessments.

In order to isolate the ear to be implanted and/or treated ear during certain test conditions (i.e. aided testing), a foam earplug and an over-the-head earmuff will be used in the contralateral (non-implanted ear). This method will be referred to in the remainder of this document as 'plug and muff.'

8.3.1 Audiometric Measures:

Standard audiometric practice and procedures are applied for the testing of inter-octave frequencies if necessary.

[figure not shown]
- Unaided air conduction thresholds using insert earphones at octave frequencies will be obtained for each ear at 250, 500, 1000, 2000, 4000 and 8000 Hz. Clinical masking used as appropriate.
- Unaided bone conduction hearing thresholds for each ear at 500, 1000, 2000 and 4000 Hz

8.3.2 Speech Perception Measures:

General speech perception testing procedures

All speech perception testing will be conducted using recorded stimuli presented from a single loudspeaker in at a minimum a single-walled sound booth capable of accommodating a calibrated, 90 degree speaker orientation. Audiometers will conform to ANSI standards for pure-tone and speech audiometry and/or Manufacturer Specifications.

Speech perception measures conducted in soundfield are to be administered via a loudspeaker at 0° azimuth at a distance of one meter from the subject. Speech signals will be presented at 60 dB A. Speech levels will be calibrated to 60 dB SPL using a microphone placed at the approximate position of the subject's head (one meter from loudspeaker).

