11.0 Efficacy Measures

Collection of efficacy data to support product approval is not part of this feasibility study. As such, no formal statistical hypothesis is being posed and/or applied. As part of this feasibility study, the following data will be collected and evaluated:

- Monosyllabic word recognition performance in quiet using the CNC word test pre-to
 post device activation at 12 months will be compared, tabulated and summarized.
 Specifically, the CNC word scores postoperatively will be compared to the pre-implant
 word score for the implanted ear. Individual and group comparisons will be completed.
 The intent is to understand the benefit of the implant treatment option and restoration
 of auditory input results in improved speech understanding.
- 2. Audiometric hearing thresholds at the 12 month postoperative test interval will be compared to preimplant thresholds. Individual and group comparison is confirmatory to assess that hearing acuity in the non-implanted ear (better hearing ear) is not affected significantly by cochlear implant treatment in the opposite ear (poorer hearing ear).
- 3. Sentence recognition scores in noise using the AzBio Sentence Test pre-to-post device activation will be compared, tabulated and summarized. Specifically, the everyday, bilateral listening condition AzBio sentence scores at the 12 month postimplant test interval will be compared to the preimplant bilateral sentence score. Individual and group comparisons will be conducted. The intent of this comparison is to evaluate the contribution and/or benefit of the implant treatment option (provision of binaural sensory input) in an asymmetrical hearing loss population.
- 4. To understand if the restoration of binaural sensory input in a single-sided deafness/asymmetrical hearing loss population results in improved ability in lateralization of sound. Using the AzBio Sentence metric, the month postimplant outcome will be compared to preoperative ability. Individual and group comparisons will be conducted.

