 - Hearing may sound different when the cochlear implant is turned on
 - Insertion of a cochlear implant electrode will likely result in the loss of any residual hearing in the implanted ear.
- Risks associated with implantation of the internal cochlear implant device and electrode array
 - The presence of a foreign body (implant) may result in irritation
 - Redness or breakdown of the skin in the area around the implant receiver/stimulator and/or rejection of the device
 - The electrode array may migrate partially resulting in reduced hearing ability
 - Misplacement of the electrode array may result in non-auditory sensations which may require additional medical treatment, surgery and/or removal of the device, however, this is considered a rare circumstance
 - Electrical stimulation may increase tinnitus, facial nerve stimulation, balance related issues (i.e. dizziness, vertigo) or pain
 - Implantation in the cochlear may preclude the use of future implant technology

- Device failure of operation that may perhaps require removal of the device
- A risk of additional loss natural hearing as a factor of chronological age (i.e. presbycusis) and/or etiology of the hearing loss may be experienced
- Any study participant experiencing a shift in audiometric threshold of 30 dB or greater pure tone average threshold shift across 250-1000 Hz from baseline to post-operative visits will be reported as an anticipated Adverse Event under this feasibility study.
- Risks specifically associated with the clinical population evaluated in this feasibility study, that of single-sided deafness/asymmetrical hearing loss

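### Do the promised counts of improved, unchanged and decreased subjects need a pre-set change criterion in Section 10?

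*Combined protocol and SAP*

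**What the plan says.** Section 10.0 states that no formal hypothesis will be tested. As a minimum, it commits to tabulating individual audiometric and speech outcomes "to establish numbers of subjects showing improvement, no change or decrease in performance". Means, medians, standard deviations and percentages are optional additions. The planned size is up to 15 subjects.

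Section 11.0 lists the comparisons of 12 months with preimplant. For CNC words in the implanted ear, "Individual and group comparisons will be completed". For thresholds, "Individual and group comparison is confirmatory to assess that hearing acuity in the non-implanted ear" is not significantly affected; no dB value, frequency set or test is attached.

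Section 8.3 says that CNC "will be used as the primary test metric for preimplant candidacy determination and follow-up postimplant performance assessments". Section 9.0 sets the baseline test at "Two lists of 50 words tested in the participant's everyday listening condition for that ear", and the 12-month visit also uses two lists of 50. Section 7.4 gives the entry limit for the ear to be implanted: "CNC word recognition score up to ≤30" per cent.

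The only numeric rule for change from baseline is in Section 12.1, where "a shift in audiometric threshold of 30 dB or greater pure tone average threshold shift across 250-1000 Hz" is to be reported as an anticipated adverse event.

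**The concern.** A three-way count needs two boundaries, and the plan gives neither. The adverse event rule cannot supply them. It looks only for loss, does not apply to speech scores and averages 250 to 1000 Hz, so a loss confined to 2000 Hz and above gives a shift of zero and a uniform 25 dB loss stays under 30 dB.

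The study is unblinded (Section 7.1), so a cut-off could be picked after the scores are known. A reader of the counts could not then separate change from retest noise. CNC is also the candidacy test. If the entry score doubles as baseline, selecting low observed scores tilts chance changes towards improvement near the 30% limit. What is at stake is the interpretation of the counts; no error rate or power claim is involved.

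**Working it through.** **1. Is there a criterion anywhere?**

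| Place | What it gives | Sorts subjects into the three classes? |
|---|---|---|
| Synopsis; Section 7.4 | 70 dB HL and 30% CNC limits | No, baseline eligibility only |
| Sections 8.3 and 9.0 | Scoring and list counts | No |
| Section 10.0 | The promise of counts | No |
| Section 11.0 | Individual and group comparisons | No |
| Section 12.1 | 30 dB, 250-1000 Hz | No, adverse event reporting only |

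The criterion is absent. Equally, no wrong criterion is stated. The plan's sample size has no derivation to reproduce.

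**2. CNC with no true change.** Inputs: 2 × 50 = 100 words per visit (Section 9.0); 15 subjects (Section 10.0). Assumptions: words independent, true score *p* from 5% to 30%. With X (baseline) and Y (12 months) independent Binomial(100, *p*), P(improved) is the sum over x of P(X = x) · P(Y > x).

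| True score | P(Y > X) | × 15 | P(any change) | P(Y = X) | P(change of 10 points or more, either way) |
|---|---|---|---|---|---|
| 5% | 0.435 | 6.5 | 0.869 | 0.131 | 0.002 |
| 10% | 0.453 | 6.8 | 0.906 | 0.094 | 0.025 |
| 20% | 0.465 | 7.0 | 0.929 | 0.071 | 0.093 |
| 30% | 0.469 | 7.0 | 0.938 | 0.062 | 0.142 |

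P(Y = X) is 1 − P(any change). If every difference counted, only 6% to 13% of truly unchanged subjects would be called unchanged. That sits badly with a plan that names no change as a class, so the large false-improvement figures describe a reading that the text does not invite.

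**3. What an ordinary criterion does.** One option is the two-term Freeman-Tukey arcsine on the observed baseline: θ(x) = arcsin√(x/101) + arcsin√((x+1)/101), with improvement called when θ(Y) − θ(X) ≥ 1.96 × √(2/100.5) = 0.2765. This requires +4, +7, +8, +10, +13 and +14 words at observed 0, 2, 5, 10, 20 and 30. False improvement is then at most 2.6%, or 0.4 of 15. A decrease cannot be reached from 0 to 3 words. Everything needed is in the two scores that will be tabulated.

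**4. CNC with a real gain.** The documents give no expected gain. Assuming true 5% at baseline and 30% at 12 months, P(improved) is:
- any difference: 1.00
- 5 points or more: 1.00
- the critical difference in step 3: 0.999
- 20 points or more: 0.86

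For a gain of that size, low or moderate cut-offs give nearly the same count. The choice matters when change is small or nil.

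**5. Selection at the entry limit.** If the baseline score is also the entry score, X is truncated at 30. With the criterion in step 3, false improvement is 2.7% at true 25%, 4.5% at true 30% and 11.6% at true 35%; a subject at true 35% passes the limit 17% of the time. A stated criterion therefore does not remove this effect. The condition need not hold for everyone, because Section 9.0 requires baseline to be re-evaluated when surgery falls more than 26 weeks after it.

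**6. Better-ear thresholds.** Assumptions: 5 dB steps, retest SD 2.5 to 5 dB per threshold, shared session SD 0 to 2 dB, 500-4000 Hz average. Among simulated unchanged ears, any worsening occurs in 37.7% to 44.6% (5.7 to 6.7 of 15), and a worsening of 10 dB or more in at most 2.1% (0.3 of 15). Here the band decides the count, and any band of sensible width removes most of the noise.

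**The case for a change.** The best case for a change is that descriptive counts still need definitions. By naming a no-change class, the plan implies a tolerance and then omits it. Section 11.0 calls the better-ear comparison confirmatory, expects the efficacy results to generalise to Medicare beneficiaries and promises publication on clinicaltrials.gov. A reader of published counts may not see the individual table, and one sentence per outcome would cost almost nothing. A flat cut-off also behaves unevenly: 10 points gives 0.2% false change at true 5% and 14.2% at true 30%.

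Part of this stands. The criterion is missing, the choice matters where true change is small, and the counts mean little unless the report says which cut-off was used.

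The rest does not carry to an amendment. The word confirmatory in Section 11.0 sits under an express statement that no hypothesis is posed, and no approval or stopping decision rests on the counts. Detailed replacement rules would be a reviewer's preferences, since they replace no stated method, and several are not ready to use:
- An exact binomial rule for lateralization change needs a true score or a rule keyed to baseline; nothing says that baseline performance is at chance.
- An AzBio band built from the trial's own between-list spread does not fix the number in advance, and it omits session variation.
- A threshold rule must handle no-response values, above all in the implanted ear, where Section 12.1 warns that "Insertion of a cochlear implant electrode will likely result in the loss of any residual hearing in the implanted ear".

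**Conclusion.** No change to the plan is needed. Section 10.0 leaves a detail open that analysts can fill sensibly: the three named classes point to a retest band, and individual scores for up to 15 subjects will be tabulated (Section 7.3 says up to 20; either way the table is small enough for any criterion to be applied and checked). No inference, error rate or power statement depends on it.

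The size is minor. The striking figure of about 7 of 15 falsely improved requires both no true change and a reading that nearly empties the no-change class. Under an ordinary critical difference it falls to at most 0.4 of 15, and under a large CNC gain the count hardly depends on a low or moderate cut-off. The residual sensitivity lies in better-ear thresholds and in CNC baselines close to 30%, and a cut-off alone would not cure the latter.

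These figures rest on independent words, the assumed true scores and gain, and the assumed threshold retest errors. The case report forms in Appendix A were not available; nothing in the text points to them for a criterion.
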